# 3.14. Study Procedures

Before implementation, the protocol and all relevant study documents including recruiting materials will be approved by the local IRB selected by the clinical site(s) and by the PHSC of FHI 360.

Participants will come to the study clinic for 1 screening visit, up to 6 pre-treatment visits, 1 enrollment/injection visit, 3 scheduled follow-up visits, a final visit, and frequent laboratory visits to draw blood samples for progesterone, estradiol, and/or MPA. The number of laboratory visits will be in the range of 22 to 72 depending on whether Part 2 is initiated, and when ovulation returns in each individual subject. The sampling schedule and duration of testing may be modified based on the interim results of Part 1 to ensure that primary and secondary outcomes are precisely measured in both parts of the study.

Study procedures and assessments for Parts 1 and 2 with their timing are summarized in Table 1. Detailed visit-specific information is provided in this section. Detailed descriptions of each assessment are provided in Section 6 (pharmacokinetic and pharmacodynamic assessments) and Section 7 (safety assessments).

Procedures and assessments	Screening	Pretreatment	Enrollment	Follow-up		
			Day 0	Day 1 to week 78		
				Scheduled Follow-up (day 7, week 13, and week 32)	Lab visits	Final visit a
Informed consent	Х					
Medical history	Х		Х			
Inclusion and exclusion criteria	Х		X			
Demographics and baseline characteristics	Х					
Height	Х		Х			
Vital signs measurement	Х		Х	Х		Х
Body weight	Х		Х	Х		Х
Breast exam	Х					Х
Urine pregnancy test b			Х			
Randomization (Part 2)			Х			
Study drug administration (injection) c			X			
Study staff assessment for ease of performing the injection			X			
Serum progesterone e, f, g		X d	Х	Х	Х	Х
Estradiol e, f, g		X d	Х	Х	Х	Х
Serum MPA h			X	Х	Х	Х
Injection site reactions i			X	Х		Х
Adverse event inquiry			X	Х	Xj	Х
Concomitant medication inquiry			Х	Х	X j	Х
Hemoglobin	Х					
Liver function testing (Part 2 only)	Х			X k		Х
Mood evaluation (Part 2 only)	Х			X k		Х
Acceptability			X	Х		Х
Menstrual bleeding pattern 				X	Х	Х
Mammogram m	Х					

Table 1:Study Procedures and Assessments (Parts 1 and 2)

- a For subjects in whom ovulation returns before month 12 post-injection, the final study visit will be scheduled at month 12. If ovulation occurs between months 12 and 18 (between weeks 52 and 78), at the time when the defining serum progesterone result becomes available, the study staff will inform the subject that she needs to return within 5 days to the investigational center for the final study visit. For subjects in whom ovulation does not return by month 18, the laboratory visit at week 78 will be considered the final study visit
- b A urine pregnancy test will be performed at enrollment; and during the study, if indicated.
- c Day 0; within the 1st 5 days of the start of subject's menstrual cycle.
- d Blood samples for serum progesterone and estradiol will be collected approximately twice weekly during the approximately 2 to 3 weeks preceding the subject's expected menses for confirmation of ovulation (ideally at least 4 measurements).
- e Blood samples for serum progesterone and estradiol will be collected on day 0 (baseline); then at day 7 and then weekly through week 32, regardless of ovulation status. If ovulation does not return by week 32, then weekly blood samples for serum progesterone and estradiol will continue to be collected until ovulation or through week 52, whichever is earlier. If there is no ovulation by week 52, then blood samples for progesterone and estradiol will be collected at weeks 61, 62, 63, 64, and 65; and at weeks 74, 75, 76, 77, and 78, if ovulation has not returned by week 65. During these additional laboratory visits, blood samples will be collected and tested for serum progesterone and estradiol at all visits, but not past return to ovulation.
- f At any time during follow-up, subjects with initial serum progesterone ≥3.0 ng/mL will be asked to return within 5 days for repeated progesterone and estradiol measurement. If repeated progesterone is at 3 ng/mL or below, the subject will continue follow-up per their visit schedule.
- g At any time during follow-up, if the serum progesterone level is ≥4.7 ng/mL, subjects will be asked to return within 5 days for repeated progesterone and estradiol measurement.
- h Blood samples for MPA will be collected on day 0; then on days 1, 2, 3, 5, 7, 10, 12, 14, 18, 21, 28, 35, and 42; then at weeks 8, 10, 12, 13, 15, 17, 19, 21, 23, 25, 26, 28, 30, and 32; and then every 28 days until week 52, regardless of ovulation status. Among subjects in whom ovulation does not return by week 52, blood samples for MPA will be collected up to 2 more times (at weeks 61 and 74), but not past return to ovulation. Blood samples will also be collected and stored for possible future MPA testing (if necessary) any time samples are collected for serum progesterone and estradiol, except for pre-treatment visits and visits for confirmation of ovulation.
- i Injection site reactions will be recorded on day 0 immediately after the injection (within 10 minutes) and within the 1st hour after injection; at days 1, 2, 3, 5, and 7; week 13 and week 32 visits; at the final visit; and at other visits, if indicated.
- j During laboratory visits, information on adverse events and concomitant medications will not be solicited, but will be documented if reported by the subject.
- k Liver function testing and mood evaluation will be evaluated at the week 13 and week 32 follow-up visits.
-  Menstrual bleeding patterns will be obtained by an interview questionnaire approximately monthly; at scheduled follow up visits (weeks 13 and 32 only); and the final study visit. In addition, in Part 2 menstrual data will be collected weekly via an on-line diary.
- m Part 1 only, prior to enrollment.

Lab=laboratory, MPA=medroxyprogesterone acetate.

#### 3.14.1. Procedures Before Study Drug Treatment

#### **Screening Visit**

Women will be referred to the investigational center through various recruitment channels which may include, but not limited to internal participant databases, advertising via internet and radio. Women who express interest to participate in the clinical study will undergo the informed consent process administered by a trained investigational center staff member including information about the study objectives, design and procedures, and potential risks and benefits of study participation.

A signed and dated informed consent form will be obtained before screening procedures commence (see Section 11.1). Women who sign the informed consent form will be assigned a

participant number and have a screening interview to obtain the following: medical history and demographic information, breast examination, blood sample for hemoglobin and liver function, height, weight, and vital signs measurements (BP, pulse, and respiration), and an interview about mood. To be eligible for Part 1 of the study all participants must have had a normal mammogram within the last year. Participants without a normal mammogram in the last year or who have an undiagnosed mass detected by breast exam during the screening visit, will have to have mammography performed to rule out breast cancer. During the screening visit, the investigational center may conduct clinical procedures per site-specific standard of care that are not required by the study protocol (eg, cervical cytology, STI testing). A subject who is screened and does not meet study entry criteria may be rescreened 1 additional time if there is a change in the subject's medical background or there is a modification to study entry criteria. If the rescreening visit occurs more than 2 months apart from the original screening visit, all screening procedures including informed consent will be repeated and a new participant number assigned.

Eligible subjects will be scheduled to return to the clinic up to 6 times for serum progesterone and estradiol measurements to confirm their ovulatory cycle (approximately twice a week preferably 3 days apart during approximately the 2 to 3 weeks preceding their next expected menses). Subjects who present for screening approximately 2 weeks prior to their next expected menses, may have their first blood sample for serum progesterone and estradiol taken on the same day.

In summary, the following procedures will be performed at screening:

- explain study purpose and procedures
- obtain written informed consent before any other study-related procedures are performed
- perform screening interview to determine eligibility and collect demographics and baseline data, including medical history
- assign participant number
- measure vital signs (BP [systolic/diastolic], pulse, and respiration)
- measure body weight and height to estimate BMI
- perform breast examination
- refer for mammography, if necessary
- interview about mood (Part 2 only)
- obtain a blood sample for liver function testing (approximately 5 mL; Part 2 only)
- obtain a blood sample for hemoglobin measurement (approximately 4 mL)

### 3.14.2. Pretreatment

Subjects who meet the inclusion/exclusion criteria at screening visit will return to the clinic approximately twice a week (preferably 3 days apart) during the approximately 2 to 3 weeks preceding their next expected menses (ideally at least 4 times) for serum progesterone and estradiol measurements to confirm ovulation. They will also have a mammogram scheduled

during this time if they have not had a mammogram within the last 12 months during Part 1 only. During these visits, blood samples will be obtained for serum progesterone and estradiol evaluation. If progesterone is at or above 4.7 ng/mL in at least 2 consecutive samples, ovulation will be considered confirmed and the subject eligible for the study. Eligible subjects will be scheduled to return to the clinic for the enrollment/injection visit during the first 5 days of her next menstrual cycle.

### 3.14.3. Procedures During Study Drug Treatment

### 3.14.3.1. Enrollment (Injection) Visit (Day 0)

The enrollment visit should take place during the first 5 days of menses. During this visit, a urine pregnancy test will be performed. Participants with hemoglobin  $\geq 10.5$  g/dL measured at screening, confirmed ovulation and negative pregnancy test will be enrolled in the study. Medications that the subjects used over the last 30 days will be documented as concomitant medications; vital signs (BP [systolic/diastolic], pulse, and respiration), and body weight will be measured and blood samples will be collected for serum MPA, serum progesterone, and estradiol before the study drug injection.

Part 1 is open-label; therefore, subjects will be assigned without randomization. The study staff allocating the study drug assignments in Part 2 will open the next sequential randomization envelope, document treatment assignment in a secure log, store the opened envelope, and communicate the assigned treatment arm to the pharmacy and/or study staff preparing and administering the injection (unless s/he is the one administering the injection).

The Part 2 investigational center staff who assigns the study drug treatment, and study staff providing the injection, will not be blinded but they will keep the subject and the rest of the investigational center staff unaware of the study drug treatment assignment. The study staff member will prepare the assigned study drug for injection according to the dilution procedures, and, unless s/he is the one administering the injection, pass it to the study staff who will inject the study drug subcutaneously in the fatty tissue over the abdomen while shielding the study drug injection from the subject's sight, as described in Section 5.1. After the injection the unblinded study staff will provide feedback on the ease of the injection administration. On the injection day the injection site will be examined for ISRs twice: within 10 minutes after the injection (by the un-blinded provider) who performed the injection; and within 1st hour after the injection (between 10 and 60 minutes) (by the blinded investigational center staff). The subject will be interviewed for acceptability of the study injection by the blinded investigational center staff. Before leaving the investigational center during the injection visit, each subject will receive the schedule of their follow-up visits.

The following procedures/assessments will be performed during enrollment/injection:

- perform urine pregnancy test (and during the study, if indicated)
- confirm eligibility
- measure vital signs (BP [systolic/diastolic], pulse, and respiration)
- measure body weight and height and estimate BMI

- (prior to injection) obtain a blood sample (approximately 15 mL) for serum MPA, serum progesterone, and estradiol
- open next opaque envelope to reveal the treatment allocation, have the pharmacist prepare the indicated dose, and deliver the syringe to the study staff (Part 2 only)
- administer study drug injection
- evaluate site of injection for an ISR after the injection twice (within 10 minutes and within 1st hour)
- document concomitant medication in the last 30 days
- document adverse events reported after the injection
- assess subject's acceptability of the injection
- assess ease of study drug injection by the study staff

The subject will remain in the clinic for at least 15 minutes after the study drug injection for observation of possible anaphylactic reactions.

For logistical reasons, study drug injection may be administered the day after other enrollment procedures are completed. When the visit is split, the blood draw and injection will occur the day after other enrollment visit procedures are conducted. The date of injection is considered "day 0."

### 3.14.3.2. Follow-up (Day 1 to Week 78)

Regardless of ovulation status, all subjects should remain in follow-up for at least 52 weeks postinjection.

There are 2 types of follow-up visits in this study: scheduled follow-up visits and laboratory visits.

### 3.14.3.2.1. Scheduled Follow-up Visits (Day 7, Month 3, and Month 7.5)

Scheduled follow-up visits will occur on day 7, month 3 (week 13), and month 7.5 (week 32) from start of study drug treatment. During these visits, in addition to collection of blood samples for serum MPA, progesterone, and estradiol, the site of study drug injection will be examined for ISR and subjects will be asked about pain, itching, and sensitivity disturbances, or other complaints at the site of injection. Measurement of vital signs and body weight will be performed. Subjects will be asked if they experienced any medical problems or took any medications since the previous report. Menstrual bleeding patterns, mood (for Part 2 only) and acceptability will be evaluated through an interview questionnaire. For Part 2, in addition to the scheduled follow-up visits menstrual bleeding patterns will be evaluated weekly through on-line diaries. For the laboratory measurement schedule, see Table 1.

The following procedures/assessments will be performed during the 3 scheduled follow-up visits:

- measure vital signs (BP [systolic/diastolic], pulse, and respiration)
- measure body weight

- obtain blood sample (approximately 15 mL) for serum MPA, serum progesterone, and estradiol
- obtain blood sample (approximately 5 mL) for liver function tests (month 3 and month 7.5, Part 2 only)
- evaluate site of injection for ISRs
- inquire about adverse events
- inquire about concomitant medication(s)
- interview about mood (month 3 and month 7.5; Part 2 only)
- interview about menstrual bleeding pattern (month 3 and month 7.5)
- interview about acceptability

### 3.14.3.2.2. Laboratory Visits

During the laboratory visits, blood samples will be obtained for serum MPA, serum progesterone, and estradiol per the sampling schedule (see Sections 3.3 and 3.4, and Table 1). In addition, the injection site will be observed for ISRs on days 1, 2, 3, and 5; and thereafter, if indicated. Information on adverse events and concomitant medications will not be solicited but documented if reported by the subject.

The following procedures/assessments will be performed during laboratory visits:

- obtain blood sample (up to approximately 15 mL) for serum MPA, serum progesterone, and estradiol per the sampling schedule
- evaluate site of injection for ISRs (on days 1, 2, 3, and 5; and thereafter, if indicated)
- interview about menstrual bleeding pattern once monthly (Part 1 only)
- document adverse event (if reported)
- document concomitant medication (if reported)

Blood samples for MPA will be collected and stored for possible future MPA testing (if necessary) any time when samples are collected for serum progesterone and estradiol, except for pre-treatment visits and visits for confirmation of ovulation.

### 3.14.3.2.3. Laboratory Visits after Week 52

Additional laboratory visits will be scheduled at weeks 61, 62, 63, 64, and 65 for all subjects in whom ovulation did not return by week 52; and at weeks 74, 75, 76, 77, and 78 if ovulation has not returned by week 65. During these additional laboratory visits, blood samples will be collected and tested for serum progesterone and estradiol (all visits) and serum MPA (weeks 61 and 74), but not past ovulation. Blood samples for MPA will be collected at all weekly visits after Week 52 and stored for possible future MPA testing (if necessary).

### 3.14.4. Procedures After Study Drug Treatment and Lost to Follow-up

## 3.14.4.1. Final Visit

Subjects will complete the study at 12 months after administration of TV-46046, or after ovulation returns (if after month 12) or at the week 78 laboratory visit (if ovulation does not return before then). If Part 2 is not initiated, subjects in Part 1 may be discontinued from the study as early as 26 weeks following study drug injection. If Part 2 is initiated, subjects will stay in the study for a minimum of 12 months (52 weeks) from start of TV-46046 treatment even if ovulation returns before then. All subjects will complete the study by 18 months (78 weeks) from the start of TV-46046 treatment even if ovulation does not return by then. Additional post-discontinuation follow-up may be considered for safety purposes until ovulation returns and/or MPA levels become undetectable.

For subjects in whom ovulation returns before month 12 post-injection, the final study visit will be scheduled at month 12. If ovulation occurs between months 12 and 18 (between weeks 52 and 78), at the time when the defining serum progesterone result becomes available, the study staff will inform the subject that she needs to return within 5 days to the investigational center for the final study visit. For subjects in whom ovulation does not return by month 18, the laboratory visit at week 78 will be considered the final study visit.

The following procedures/assessments will be performed during the final visit:

- obtain blood sample for serum MPA (approximately 5 mL)
- obtain blood sample for serum progesterone, estradiol (approximately 10 mL), if indicated; and liver function tests (Part 2 only, approximately 5 mL)
- measure body weight
- measure vital signs (BP [systolic/diastolic], pulse, and respiration)
- perform breast exam
- interview about acceptability
- evaluate site of injection for ISRs
- inquire about adverse events
- inquire about concomitant medications
- interviews about mood (Part 2 only) and menstrual bleeding pattern

If the subject cannot return to the investigational center in person, the final evaluation may be completed by telephone (to the extent possible) and documented in the CRF.

For subjects who withdraw prematurely from the study, the final visit will be performed at the time of discontinuation, if known.

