
Study participation will consist of a screening and pre-treatment phase (approximately 1 month, or 4 weeks), a treatment phase (6 months, or 26 weeks), and post-treatment follow-up (an additional 6 to 12 months). During the pre-treatment phase, ovulation will be confirmed in all subjects who are otherwise eligible for the study by measuring serum progesterone twice a week (preferably 3 days apart) during the 2 to 3 weeks preceding expected menses. Enrolled subjects will receive an injection of the study drug and then be followed for at least 12 months (52 weeks) to characterize pharmacodynamics and pharmacokinetics of MPA (ie, 6 months of treatment plus 6 months of post-treatment follow-up), regardless of earlier return to ovulation. There will be three in-depth scheduled follow-up visits at day 7, week 13, and week 32 after injection, as well as frequent, brief laboratory visits that include collection of blood samples.

Subjects in both parts of the study will be routinely evaluated for vital signs, body weight, and acceptability (ie, responses to questions about injection pain, ISR complaints, and menstrual bleeding patterns), and will provide blood samples for serum progesterone, estradiol, and MPA at frequent predefined time points for 12 months (52 weeks) from start of study drug administration (regardless of earlier return to ovulation). Subjects who have not ovulated by month 12 (week 52) will be monitored by less frequent measurements of serum progesterone, estradiol, and MPA until ovulation returns for safety reasons for up to another 26 weeks (up to a total of 78 weeks from the injection of study drug). Injection sites will be observed for ISRs on the day of the study drug injection (day 0), post-injection at days 1, 2, 3, 5, and 7, week 13, week 32, at the final study visit, and other visits, if indicated. The subject's menstrual bleeding pattern will be ascertained by interviewer-administered questionnaire at monthly intervals during scheduled laboratory visits (in Part 1 only), at two scheduled follow-up visits (weeks 13 and 32 only), and at the final study visit. In addition, during Part 2 the subject's menstrual bleeding patterns will be ascertained weekly using an on-line diary; and liver function testing and mood assessment will be done at screening,

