Study participation will consist of a screening and pre-treatment phase (approximately 1 month, or 4 weeks), a treatment phase (6 months, or 26 weeks), and post-treatment follow-up (an additional 6 to 12 months). During the pre-treatment phase ovulation will be confirmed in all subjects who are otherwise eligible for the study by measuring serum progesterone approximately twice a week (preferably 3 days apart) during the approximately 2 to 3 weeks preceding expected menses. Enrolled subjects will receive an injection of the study drug and then be followed for at least 12 months (52 weeks) to characterize pharmacodynamics and pharmacokinetics of MPA (ie, 6 months of treatment plus 6 months of post-treatment follow-up), regardless of earlier return to ovulation.

During the study, subjects will provide blood samples for serum progesterone, estradiol, and MPA at frequent pre-defined time points (see Table 1 for the study procedures and assessments).

In addition to frequent laboratory visits to collect blood samples, there will be 3 scheduled follow-up visits: at day 7, month 3 (13 weeks), and month 7.5 (32 weeks) after start of study drug treatment, during which subjects will be weighed and evaluated for ISRs, vital signs, and acceptability. Injection sites will be observed for ISRs on days 0 (within 10 minutes and within the 1st hour after injection), 1, 2, 3, and 5; at 3 scheduled follow-up visits (at day 7, week 13, week 32); at the final study visit, and at other visits, if indicated. The subject's menstrual bleeding patterns will be obtained by an interview questionnaire at monthly intervals (in Part 1 only), by weekly diary completed by the subjects on-line (in Part 2 only), and at follow-up visits (month 3 and month 7.5 only), and the final study visit. In Part 2 only, liver function will be assessed by tabulating and graphing change in liver function tests including but not limited to ALT and AST, from screening to week 13 (month 3), week 32 (month 7.5), and final study visits. Information on adverse events and concomitant medicines will be collected throughout the study. The study staff will provide assessment on the ease of the injection.

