# **3.3.** Pharmacokinetic Measures and Time Points

The primary pharmacokinetics measure is serum MPA concentration. For Part 1, blood samples for measurement of serum concentrations will be obtained on days 0 (baseline), 1, 2, 3, 5, 7, 10, 12, 14, 18, 21, 28, 35, and 42; weeks 8, 10, 12, 13, 15, 17, 19, 21, 23, 25, 26, 28, 30, and 32; and then every 28 days until week 52, regardless of ovulation status.

Among subjects in whom ovulation has not returned by month 12 (week 52), blood samples for MPA will be tested up to 2 more times (once at week 61 and once at week 74), but not past return to ovulation. The sampling schedule and duration of MPA testing may be modified based on accumulating data for a more accurate characterization of the pharmacokinetic profile of TV-46046. In addition, blood samples will also be collected and stored for possible future MPA testing (if necessary) at all weekly visits when samples are collected for serum progesterone and estradiol, except for pre-treatment visits and visits for confirmation of ovulation.

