LOQ	limit of quantification
MedDRA	Medical Dictionary for Regulatory Activities
MOP	manual of procedures
MPA	medroxyprogesterone acetate
P	Progesterone
SD	standard deviation
SOC	system organ class
t _{1/2}	Apparent terminal half-life
t _{max}	time to maximum serum drug concentration
WY	Women-years

INTRODUCTION

This Statistical Analysis Plan (SAP) describes the planned analysis and reporting for A Two-part, Phase 1, Exploratory and Dose-range Finding Study to Evaluate Suppression of Ovulation and Pharmacokinetics of Medroxyprogesterone Acetate Following a Single Subcutaneous Administration of TV-46046 in Women with Ovulatory Cycle. The study is sponsored by Teva Branded Pharmaceutical Products R&D, Inc. and implemented by FHI 360. Version 1.0 of the SAP was written and approved prior to first subject enrolled.

The reader of this SAP is encouraged to review the study protocol for details on the conduct of the study, the operational aspects of clinical assessments, and the timing for completing the participation of a subject in this study. The SAP is intended to be in agreement with the protocol, especially with regards to the primary and secondary endpoints and their respective analyses. However, the SAP may contain more details regarding these particular points of interest, or other types of analyses (eg, other endpoints). When differences exist in descriptions or explanations provided in the study protocol and this Statistical Analysis Plan, the SAP prevails; any differences between the two will be explained in the Clinical Study Report (CSR).

Changes made to the SAP after study initiation (other than formatting for regulatory submissions), including changes made to address revisions to the protocol, will be documented in Section 13. Mock tables, figures and listings designed to capture the results of analyses specified here will be approved by the Coordinating Investigator prior to un-blinding of statisticians, and included in an appendix to future versions of the SAP.

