2. STUDY DESIGN

This is a 2-part study designed to evaluate the pharmacokinetics and pharmacodynamics of MPA in healthy female subjects after a single subcutaneous injection of TV-46046. Part 1 is a non-randomized component which will explore the pharmacokinetics of a 120 mg dose of MPA when TV-46046 is administered at an undiluted concentration of 400 mg/mL (0.3 mL injection volume) or a 1:1 saline-diluted concentration of 200 mg/mL (0.6 mL injection volume). Cohorts of n=6 participants will be enrolled in sequential order: undiluted drug followed by 1:1 saline diluted drug. If results indicate that information on an intermediate concentration is required to characterize pharmacokinetics, then a 3rd cohort of 6 participants may be administered TV-46046 at a concentration of 300 mg/mL (0.4 mL injection volume).

Part 2 is a randomized, multi-center, dose-range finding component which will only be implemented if undiluted TV-46046 is selected for further testing based on Part 1 data. Criteria used to select each of up to 3 doses of undiluted TV-46046 in the range of 80 to 300 mg for Part 2 include: mean C_{max} predicted to be less than 3 ng/mL, time to achieve 0.2 ng/mL predicted to be no more than 24 hours after study drug administration, 6-month serum MPA concentration predicted to be greater than 0.1 ng/mL for 95% of women, and serum MPA concentration 24 months after last injection predicted to be below 0.1 ng/mL in 90% of women. As only a 120 mg dose of TV-46046 will be tested in Part 1, predictions about the pharmacokinetics of Part 2 doses will be partly informed by dose relationships observed in previous studies of depot medroxyprogesterone acetate (DMPA) delivered subcutaneously. The final study size for Part 2 will be informed by Part 1, but will not exceed 20 women per dose group (including 2 obese women per group).

Each subject enrolled in either Part 1 or Part 2 will contribute up to 19 months in the study, including up to 1-month pre-treatment, 6-months treatment, and 6-12 months of post-treatment follow-up. Study procedures and assessments with their timing are summarized in Table 1 of the study protocol.

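### Does the option to release Part 1 women from week 26 contradict the 52-week follow-up and empty the later Part 1 outputs?

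*Protocol*

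**What the plan says.** Section 3.14.4.1 of the protocol contains the permissive clause: "If Part 2 is not initiated, subjects in Part 1 may be discontinued from the study as early as 26 weeks" after injection. It then says that if Part 2 is initiated, women stay at least 12 months. Section 3.11 repeats the pair as total participation: about 30 weeks if Part 2 is not initiated, about 56 weeks if it is.

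Elsewhere the protocol states a longer minimum without pointing to that clause. Section 3.1 has subjects "followed for at least 12 months (52 weeks) to characterize pharmacodynamics and pharmacokinetics of MPA", and the synopsis matches it. Section 3.14.3.2 says: "Regardless of ovulation status, all subjects should remain in follow-up for at least 52 weeks postinjection". Section 3.3 schedules Part 1 MPA samples to week 32 "and then every 28 days until week 52, regardless of ovulation status".

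The synopsis and Section 3.1 also carry a second early-stop clause. Part 1 women may be discontinued if the interim data show that no concentration, diluted or undiluted, merits further work. This clause gives no minimum week.

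SAP Section 2 says: "Each subject enrolled in either Part 1 or Part 2 will contribute up to 19 months in the study", made up of up to one month of pre-treatment, "6-months treatment, and 6-12 months of post-treatment follow-up". The SAP Introduction adds: "When differences exist in descriptions or explanations provided in the study protocol and this Statistical Analysis Plan, the SAP prevails". SAP footnote 1 and Section 13.3 record that Part 2 was never implemented. The Part 1 pharmacokinetics were favorable, and the reasons given are stability, syringeability and manufacturing.

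**The concern.** Two sets of passages give different minimum follow-up for the same women, and the two early-stop clauses have different triggers. The recorded facts separate those triggers. Part 2 did not start, so the week-26 clause is available. The pharmacokinetics were favorable, so the other clause appears not to be met. A manufacturing decision about Part 2 could therefore end Part 1 sampling.

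Several SAP outputs that are not limited to Part 2 need data after week 26:

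- observed C210 (Section 10);
- month-7.5 vital signs and acceptability (Sections 8.8 and 9);
- the month-12 mean used to predict accumulation (Section 10);
- time to ovulation, censored at month 12 (Sections 11.1 and 11.2);
- the probability of return to ovulation after month 12 (Section 8.4).

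Relating MPA concentration to return of ovulation is a secondary objective for both parts (protocol Section 2.2.2). Part 1 is now its only source of data.

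**Working it through.** **1. The plan's own durations.** Pre-treatment is about 4 weeks. 4 + 26 = 30 and 4 + 52 = 56 reproduce the two minima in Section 3.11, and 4 + 78 = 82 reproduces its maximum. For the SAP, 1 + 6 + 12 = 19 months is a maximum. The 12-month minimum (6 + 6) is implied, not stated.

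**2. Is the week-26 exit built into the plan?** Section 3.14 gives 22 to 72 laboratory visits and ties the range partly to whether Part 2 starts. The MPA schedule has 32 post-dose times to week 52, of which 24 fall by day 182. Taking out day 7 and week 13, which are scheduled follow-up visits, leaves 24 − 2 = 22, the stated lower bound. With 52 weeks of follow-up, MPA sampling alone needs 32 − 3 = 29 laboratory visits (28 if week 52 is the final visit), so 22 cannot be reached. The protocol does not show its count, so this match is an inference. Adding the current weekly progesterone visits gives 31 to week 26.

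**3. Samples forgone if every woman left at week 26.** MPA: weeks 28, 30, 32, 36, 40, 44, 48 and 52, or 8 of 32. Progesterone: up to 26 of 52 weekly samples, 6 due from all women and 20 due only until ovulation. C182 and AUC0-182 are still observed. C210 is not: day 210 less the 84-hour analysis window is day 206.5.

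**4. How informative the late MPA samples are.** The inputs are for Depo-subQ 104 (protocol Section 1.1): Cmax 1.56 ng/mL and half-life 43 days. The peak is taken at day 7 (Section 1.3.2.1) and the LOQ is 0.02 ng/mL (Section 6.1.4).

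- The LOQ is reached at 7 + 43 × log2(1.56/0.02) ≈ day 277, so about 4 of the 8 samples would be quantifiable. At assumed half-lives of 60 to 90 days all 8 would be.
- The terminal-slope rule of SAP Section 14 was simulated with 1,500 subjects per setting, an assumed 2-day absorption half-life and residual CV of 15% or 25%. At 43 days, the median ratio of estimated to true half-life is 0.991 or 0.972 with data to day 182, against 1.005 or 1.001 with data to week 48.
- At an assumed 90 days the ratios are 0.951 or 0.882, against 0.985 or 0.950.

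**5. Ovulation.** The inputs are for a single dose of the same marketed product: median 212 days (Section 1.4.2) and 90% suppression at 150 days (Section 1.5). A log-normal time to ovulation is assumed.

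- SD = ln(212/150)/1.2816 = 0.270.
- Not ovulated by day 182: Φ(ln(212/182)/0.270) = 0.714. By day 364: 0.023.
- Expected ovulations in 12 women: 12 × 0.286 = 3.4 by week 26, and 12 × 0.977 = 11.7 by week 52. For SD 0.2 to 0.4 these are 2.7 to 4.2 and 10.9 to 12.0.
- In a group of 6, the Kaplan-Meier median is not reached if at least 4 have not ovulated by day 182: probability 0.77 (0.64 to 0.87).
- After week 52: 12 × 0.023 ≈ 0.3 woman.

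**6. Price of removing the option.** Each woman would keep 11 visits in weeks 27 to 52 (weeks 27 to 32 plus five later MPA visits) to 26 visits. For 12 women that is 132 to 312, plus up to 10 visits after week 52 for each woman who has not ovulated.

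**The case for a change.** The strongest case for a change is that the exception is stated twice with different triggers, and this study falls between them. The sentence in Section 3.14.3.2 covers all subjects and does not mention Part 2. Sections 3.12 and 4.4 have staff tell women that staying until delayed return to ovulation has been assessed is important, which a week-26 exit would prevent. Follow-up after such a stop is discretionary under Section 3.14.4.1. The ovulation loss in step 5 is large.

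Much of this is answered by reading the text in order:

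- The 52-week sentences hold whether or not a woman has ovulated. They stop women leaving because ovulation has returned. The case where Part 2 does not start is handled in Sections 3.11 and 3.14.4.1, which give each branch its own minimum.
- In Section 3.1 and the synopsis, the other early-stop clause comes just before the 52-week text, so neither passage stands without an exception.
- The SAP figure is a maximum, and the Introduction that gives the SAP precedence also sends the reader to the protocol for the timing of participation.

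What stands is that the two triggers are not harmonised or cross-referenced. If the option were used, the month-12 mean and the month-7.5 summaries would have no substitute at the planned time. Other outputs are partly covered: a final visit at discontinuation collects vital signs and acceptability, profiles run to withdrawal, and SAP Section 14 imputes partial-AUC end-times.

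**Conclusion.** No change follows. The text is a 52-week default with a deliberate, permissive exception, imperfectly cross-referenced. An analyst would not be misled: women who leave early are censored at departure, and outputs without data are reported as unavailable.

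The loss arises only if the option is used, and nothing in the documents shows that it was. SAP version 2.0, which records that Part 2 was dropped, still treats month 12 as the end of routine pharmacokinetic testing. If the option were used, the day-182 endpoints would be intact and the half-life bias would be about −1 to −3% at the 43-day half-life, but most ovulation data would be lost (about 3.4 events against 11.7 in 12 women). That last figure rests on a two-point log-normal fit to another product at 104 mg. The probability of ovulation after week 52 would lose little, about 0.3 woman in 12.

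Removing the option would not secure the data either. Section 3.12 lets the sponsor reduce the scope or stop the study with no minimum week. Weighing 132 to 312 visits and sponsor flexibility against exploratory results in a part not sized for definitive conclusions (protocol Section 8.1) is a fair trade-off that statisticians could settle either way. Aligning the triggers and adding cross-references would tidy the protocol but alter no analysis. This review takes no position on which follow-up rule should prevail.
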